## 1. PURPOSE OF THE STUDY

---

### a. Brief Summary

Recurrent pregnancy loss and unexplained infertility are emotional and difficult diagnoses for patients. Despite a thorough medical investigation, most cases of recurrent pregnancy loss remain unexplained and unexplained infertility is by definition so. Understanding endometrial factors that may contribute to recurrent pregnancy loss and unexplained infertility are of increasing interest. The purpose of this study was to determine if patients with recurrent pregnancy loss or unexplained infertility have altered gene expression in the uterus, or an altered microbiome, during the window of implantation and to assess whether luteal phase progesterone supplementation improves or alters gene expression and to assess whether oral antibiotics followed by vaginal probiotics improves an altered microbiome.

---

### b. Objectives

The investigators hope to determine if endometrial gene expression is altered in recurrent pregnancy loss or unexplained infertility patients compared to healthy controls. Furthermore the investigators hope to learn if luteal phase progesterone support normalizes women with altered endometrial gene expression and if oral antibiotics and over the counter vaginal probiotics improve an altered uterine microbiome. This would give us better evidence to justify using progesterone support which is often done empirically without strong evidence for or against and suggest a uterine mechanism of an altered microbiome in infertility and recurrent pregnancy loss. This knowledge would provide a better means to counsel patients in these populations.

---

### c. Rationale for Research in Humans

Human subjects must be used for this study as the purpose of the study is to understand human endometrial genetic expression and the human microbiome in an unexplained recurrent pregnancy loss and unexplained infertility patient populations. Furthermore this is a minimal risk study where patients are already undergoing endometrial biopsies as a

standard of care to rule out endometrial infection. For healthy controls this is a minimal risk study as the endometrial biopsy is a minimal procedure. The benefit to the healthy controls would be access to the information which may be relevant to them in their future reproductive attempts.

---

## **2. STUDY PROCEDURES**

---

### **a. Procedures**

Patients enrolled in the study will be those presenting to the clinic for evaluation and treatment of recurrent pregnancy loss and infertility. Healthy controls will be patients presenting for elective egg freezing and elective sex selection and recruited from the general population by way of flier.

Recurrent pregnancy loss and infertility patients will undergo the routine clinical standard evaluation including a uterine cavity evaluation, evaluation for endometritis, ovarian reserve testing, and for patients with recurrent pregnancy loss also parental chromosome analysis, antiphospholipid antibody blood testing and thyroid screening. Egg freezing patients will undergo routine clinical evaluation which includes uterine ultrasound evaluation and ovarian reserve testing and elective sex selection patients will undergo a routine evaluation which includes a uterine cavity evaluation, ovarian reserve testing and blood testing.

For new patients presenting with no prior evaluation we will perform the uterine cavity evaluation as per standard of care in the follicular phase of the menstrual cycle. The endometrial biopsy is typically done during this same appointment however the endometrial biopsy will be deferred for the purposes of the study in order to perform the endometrial biopsy during the window of implantation after ovulation. This endometrial biopsy will be sent to pathology to rule out endometritis as per clinical standard of care and will allow us to evaluate endometrial gene expression during the window of implantation. The endometrial sample will be sent to Ivigen for an endometrial receptivity array (ERA) and microbiome analysis at no extra cost to the patient. The ERA provides information on the receptivity of a patient's endometrium to the implantation of an embryo. It is hypothesized that unexplained recurrent pregnancy loss and unexplained infertility patients are more likely to have a nonreceptive endometrium than healthy historic controls.

For return patients with prior standard evaluation they will be invited to participate in the study. These patients will undergo an endometrial biopsy as above. The endometrial sample will be sent to Ivigen to our collaborators ([name]) for an endometrial receptivity array (ERA) and microbiome analysis at no extra cost to the patient. [name] group will perform the analysis of the sample.

For patients whose ERA shows a non receptive endometrium in the subsequent menstrual cycle, vaginal progesterone medication which is often prescribed empirically for recurrent pregnancy loss will be prescribed to start 3 days after ovulation detected by home urine LH kits. A second endometrial biopsy will be sent for a repeat ERA at not

extra cost to the patient. The patient will still be able to participate in the study if they decline this second biopsy.

For patients who microbiome is altered, a 2 week course of oral doxycycline will be prescribed followed by 2 weeks of over the counter vaginal probiotics. A second endometrial biopsy will be sent for a repeat microbiome at not extra cost to the patient. The patient will still be able to participate in the study if they decline this second biopsy.

If on the first biopsy there is endometritis the patient will first be treated based on standard of care practice with routine use of oral antibiotics prior to undergoing a second endometrial biopsy which is also routine practice. If the microbiome or ERA is also abnormal (It would be for example EXPECTED that the microbiome will be altered in all endometritis patients) for an abnormal ERA- vaginal progesterone would be added prior to rebiopsy and/or vaginal probiotics would be added.

The patients' follow up visits and treatment regimens will be determined by the treating physician according to the standard of care treatment of recurrent pregnancy loss, unexplained infertility or other medical comorbidities.

These patients are not required to consent to any additional testing or drug treatments outside of that which is standard treatment of their condition(s). They will consent to follow up communication (phone call or email) for up to 5 years after enrollment in the study to allow for completion of data collection and pregnancy outcomes except for the healthy controls who will be followed for 1 year.

The only procedures which would be considered entirely research would be sending the endometrial biopsy tissue for ERA testing (currently endometrial biopsy is a standard of care for recurrent pregnancy loss and unexplained infertility) however this is not sent for ERA testing.

Empiric use of vaginal progesterone is often used in the setting of recurrent pregnancy loss and unexplained fertility however doing a repeat biopsy in this setting would be considered research- not standard of care.

Use of antibiotics is often used in the setting of non-specific findings for endometritis in recurrent pregnancy and unexplained fertility however using this in the setting of an abnormal microbiome in combination with over the counter vaginal probiotics would be considered research.

---

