**g. Study Endpoint(s)**

For patients who are found to have a receptive endometrium, the study end point will be after the standard medical evaluation as described. For patients who are found to have a non receptive endometrium or abnormal microbiome the study end point will be after the second endometrium biopsy. Participants will be allowed to continue any standard

medically indicated treatments throughout the study. For healthy controls the study end point will be after the first endometrial biopsy and we will not plan a repeat biopsy. The study will end once the anticipated total number of participants is met to complete an adequate power analysis.

---

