### a. Planned Enrollment

The number of participate expected to be enrolled at Stanford Medicine Fertility and Reproductive Health Clinic is 100 patients per patient population (100 recurrent pregnancy loss patients, 100 unexplained infertility patients and 100 health controls). Any patients eligible for the study but desiring no intervention will be offered the alternative of being included as an observational group only without intervention in order to compare pregnancy outcomes without intervention. These patients will be recurrent pregnancy loss and unexplained infertility patients seeking treatment at our facility. healthy controls will be patients presenting for elective egg freezing and sex selection.

---

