**h. Eligibility Criteria**

i. Inclusion Criteria

Subjects must fulfill the following inclusion criteria to be eligible to participate in the study:

1. Have a diagnosis of recurrent pregnancy loss as defined as two or more unexplained pregnancy losses at less than 10 weeks (miscarriages with known chromosomal errors excluded) OR have a diagnosis of unexplained infertility defined as normal ovarian reserve testing, normal ovulatory function, normal semen analysis defined why WHO criteria and evidence of at least one patent fallopian tube.
2. Agree to the standard of care testing for evaluation of recurrent pregnancy loss OR unexplained infertility OR routine testing for preparation for oocyte freezing or elective sex selection.
3. Be at least 18 years old and less than 46 years old.
4. Have menstrual cycles that occur in 25-35 day intervals
5. Agree to follow up for 5 years from the date of enrollment

ii. Exclusion Criteria

1. Irregular menstrual cycles
2. Presence of untreated submucosal fibroids or polyps
3. an unligated hydrosalpinx
4. non-ovulatory progesterone level on the day of endometrial biopsy
5. Women <21 or >45 years old.

---

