**c. Procedures to Minimize Risk**

Clinical study staff will explain all procedures thoroughly to consented subjects and why each diagnostic test is being done during their evaluation. There are no anticipated

additional risks to a patient who is involved in this study as compared to a nonparticipating patient in the same clinical setting. Subject identity will be kept confidential.

---

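### The study moves the biopsy from the follicular phase to the window of implantation in women seeking pregnancy, but the no-added-risk statements do not cover that change and the protocol text does not address possible conception in the biopsy cycle

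*Protocol*

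**What the plan says.** Protocol 2.a describes routine practice for new patients: the uterine cavity is evaluated in the follicular phase, and "The endometrial biopsy is typically done during this same appointment". The study departs from this. The biopsy "will be deferred for the purposes of the study in order to perform the endometrial biopsy during the window of implantation after ovulation". Return patients, already evaluated, are invited to a biopsy done the same way.

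On who is affected, 2.a states: "Patients enrolled in the study will be those presenting to the clinic for evaluation and treatment of recurrent pregnancy loss and infertility". Section 7.a plans "100 recurrent pregnancy loss patients, 100 unexplained infertility patients and 100 health controls".

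Section 7.h requires regular cycles ("Have menstrual cycles that occur in 25-35 day intervals") and lists as an exclusion a "non-ovulatory progesterone level on the day of endometrial biopsy".

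On risk, 2.b says that new patients meet no research procedure beyond usual care, and 8.c says that the investigators anticipate no "additional risks to a patient who is involved in this study as compared to a nonparticipating patient" in the same clinic. Section 2.a, however, classes a repeat biopsy after progesterone as research and not usual care. Section 2.g makes that repeat biopsy an end point: "For patients who are found to have a non receptive endometrium or abnormal microbiome the study end point will be after the second endometrium biopsy".

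**The concern.** A biopsy in the follicular phase precedes ovulation, so it precedes any conception in that cycle. A biopsy in the window of implantation follows ovulation and falls, by the protocol's own term, when an embryo would implant. The study makes this change, and makes it in women who come to the clinic because they want a pregnancy. Those with recurrent loss have conceived at least twice. Those with unexplained infertility must have normal ovulation and an open tube.

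The no-added-risk position relies on participants receiving the same care as other patients of the clinic. For the timing of the first biopsy, and for the research repeat biopsy, they do not. An ethics committee or participant reading 2.b and 8.c would not learn that the study itself places the biopsy where a conception in the same cycle is possible.

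**Working it through.** The protocol has no figure to reproduce on this point. It gives no conception rate, and the 100 per group in 7.a comes without a rate, effect size or power. The check is therefore mainly a comparison of sections, followed by a rough scale.

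**1. Timing against the risk statements**

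- 2.a: the biopsy of new patients is moved from before to after ovulation, for study purposes.
- 2.b: new patients have nothing outside usual care. This is true of the biopsy as a procedure, but not of its timing.
- 2.a: the repeat biopsy after progesterone is research. It is offered to any patient with a non-receptive result, new patients included.
- 8.c: no added risk is anticipated compared with a non-participant. A non-participant would have had the biopsy at the follicular-phase visit, and no research repeat.
- 8.a: the repeat biopsy is mentioned, as optional and of minimal physical risk. Cycle phase is not.

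The statements in 2.b and 8.c cannot both stand as worded beside 2.a.

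**2. Does the protocol address conception in the biopsy cycle?**

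- 7.h (eligibility): covers diagnosis, agreement to testing, age, cycle length, follow-up, fibroids or polyps, hydrosalpinx and biopsy-day progesterone. Conception is not covered. The progesterone criterion is the only one tied to the biopsy day. It selects ovulatory cycles, which are the cycles in which conception is possible.
- 2.a (procedures) and 7.i (screening): nothing on conception in a biopsy cycle.
- 2.b, 8.a, 8.c and 8.e (risks and monitoring): complications and side effects are listed, but not this situation.
- 2.e: treatment may be delayed by one to two months. This concerns starting treatment and is not a statement about attempts to conceive.

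**3. Scale, under stated assumptions**

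Inputs: 100 recurrent-loss and 100 unexplained-infertility patients (7.a), one first-biopsy cycle each. Assumptions not in the documents: every case is attempting conception in that cycle, and the per-cycle probability c lies between 2% and 15%, lower in unexplained infertility.

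Expected conception cycles = sum over groups of n × c:

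- split by group: 100 × 0.02 + 100 × 0.15 = 2 + 15 = 17
- 2% in all: 200 × 0.02 = 4
- 15% in all: 200 × 0.15 = 30

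Below that range, at c = 1%, the expected number is 200 × 0.01 = 2, and the chance of at least one is 1 − 0.99^200 = 0.87. If only some of the cases are attempting conception, every expected number shrinks in proportion.

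**The case against.** The strongest reply is that silence in these sections does not prove there is no safeguard. The consent pages were not part of the text reviewed, and an instruction could stand there. This is correct, and the point is limited accordingly. It does not rescue 2.b and 8.c, which are worded without regard to the change of phase whatever the consent form says.

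A second reply is that 2.e, with its delay of one to two months, suggests the biopsy cycles are not treatment cycles. That is fair for assisted or empiric treatment. It does not bear on natural conception, and 2.g allows standard treatments to continue.

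A reader might also infer more than the documents support:

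- **That every study biopsy falls in the window of implantation.** Section 2.a gives no cycle phase for the repeat microbiome biopsy or for the re-biopsy after endometritis, and 7.h does not say that the progesterone criterion applies to repeats.
- **That the biopsy would harm an early pregnancy or distort the profile in a conception cycle.** The documents say neither, and the point does not depend on either.
- **That women who conceive drop out and bias the repeat-biopsy result.** This is a secondary inference of unknown size. A woman who conceived between biopsies would lack one measurement, but 2.a keeps patients who decline the second biopsy in the study and follows pregnancy outcomes for up to 5 years. One who conceived in the repeat cycle might be sampled unrecognised. How a missing repeat measurement is handled belongs in the SAP, which was not available.
- **That about 30 conception cycles should be expected.** That figure needs 15% in both groups, which conflicts with assuming a lower rate in unexplained infertility.

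**Conclusion.** The point holds in a limited form. The study moves the biopsy of women seeking pregnancy to after ovulation and adds a research repeat biopsy. The protocol text reviewed does not address possible conception in the biopsy cycle, and 2.b and 8.c state a usual-care, no-added-risk position that does not cover either change. The inconsistency between these sections and 2.a stands at any conception rate.

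The number of cycles concerned cannot be derived from the documents. About 17 of 200 first-biopsy cycles is an illustration, with 4 to 30 as its range; it assumes the rates given and that all cases are attempting conception. The exposure concerns the two patient groups. The healthy controls are not described as trying to conceive and have no planned repeat biopsy, although no criterion addresses them either.

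This is more than a missing detail, because following the protocol as written carries out the study-driven biopsy under a risk statement that does not describe it.

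**What to change.** - Reconcile 2.b and 8.c with 2.a, so that the risk statement covers both the study-driven change of cycle phase and the research repeat biopsy.
- Have 2.a or 7.h address possible conception in a biopsy cycle. What the rule should be is for the investigators to decide. If the consent form already contains one, the protocol should state it too.
- Keep the consent wording consistent with the revised text.

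The cost is a few lines of text and a slightly less favourable risk statement. No new procedure follows from the reconciliation itself, and the planned 100 per group is unaffected. The handling of a repeat biopsy not taken because of conception can be left to the SAP.

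### The repeat-biopsy aims claim a treatment effect, but no untreated re-test is planned; restate them as uncontrolled before-after descriptions (clearest for the microbiome, weaker for ERA)

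*Protocol*

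**What the plan says.** Sections 1.a, 1.b, 3.a and 8.a of the protocol state treatment aims. One is whether luteal progesterone normalises or improves endometrial receptivity. The other, in 1.a and 1.b, is whether antibiotics plus probiotics improve an altered microbiome. Section 1.b adds that the result would strengthen the evidence for using progesterone, and 8.a gives the repeat ERA the purpose of determining whether progesterone improves receptivity.

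Section 2.a gives the sequence. After a non-receptive first ERA, progesterone is prescribed in the next cycle and "A second endometrial biopsy will be sent for a repeat ERA". After an altered microbiome, "a 2 week course of oral doxycycline will be prescribed followed by 2 weeks of over the counter vaginal probiotics", and then "A second endometrial biopsy will be sent for a repeat microbiome at not extra cost to the patient". Women with endometritis are "treated based on standard of care practice with routine use of oral antibiotics prior to undergoing a second endometrial biopsy", with progesterone and/or probiotics added if the ERA and/or microbiome is also abnormal. The second biopsy may be declined.

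Section 2.g says that for women with a "non receptive endometrium or abnormal microbiome the study end point will be after the second endometrium biopsy". It also says: "For healthy controls the study end point will be after the first endometrial biopsy and we will not plan a repeat biopsy". Section 7.a lets eligible women who want no treatment be "included as an observational group only without intervention in order to compare pregnancy outcomes without intervention". Section 9 asserts that ERA is consistent across cycles; nothing similar is said of the microbiome.

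**The concern.** Every woman who is re-tested was chosen because her first result was abnormal. On a normal/abnormal score such a group can only stay abnormal or become normal, so test error and natural fluctuation push the result in one direction, the same one that a working treatment would. Scoring on a continuous scale does not help, because values selected for being extreme tend to move back towards the mean.

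Separating this drift from a treatment effect needs to be informed by how often comparable untreated women become normal at re-test. If that is unknown, a change towards normal would be read as an effect of treatment. At stake are the conclusions on both repeat-biopsy aims, and the use of the findings in counselling, which section 1.b names as a goal. The comparison of first biopsies between patients and controls is not affected.

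**Working it through.** The protocol gives no re-test agreement, no expected abnormal rate and no target for these aims, so there is no figure to reproduce. The check has three steps.

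**1. Is an untreated re-test planned anywhere?**

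| Group | Treated before re-test? | Repeat ERA or microbiome? | Protocol section |
|---|---|---|---|
| Non-receptive ERA | Yes, progesterone | Yes | 2.a, 8.a |
| Altered microbiome | Yes, antibiotics then probiotics | Yes | 2.a |
| Endometritis | Yes, antibiotics, with additions if a test is abnormal | Yes | 2.a |
| Receptive patients | Not applicable | None stated on account of ERA | 2.g |
| Healthy controls | No | None planned | 2.g |
| Observational group | No | None described; purpose is pregnancy outcomes | 7.a |

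No row supplies an untreated re-test in women with an abnormal first result.

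**2. Can the treatment effect be recovered from the treated women alone?** Let c be the observed proportion converting to normal, r the proportion who would have converted untreated, and e the proportion converted by treatment among those who would otherwise stay abnormal. If treatment does not hinder spontaneous reversion, then

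c = r + (1 − r)e, so e = (c − r)/(1 − r).

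Take c = 0.40 (assumed):

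- r = 0 gives e = 0.40
- r = 0.20 gives e = 0.20/0.80 = 0.25
- r = 0.40 gives e = 0

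The planned data estimate c and nothing estimates r, so these three cases look identical.

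**3. How much could this matter?** All inputs here are assumed except the 200 patients (100 + 100, section 7.a). If the abnormal prevalence p is the same at both tests and re-test agreement is kappa, the untreated conversion rate is (1 − p)(1 − kappa). With p = 0.30 there are 200 × 0.30 = 60 abnormal women. If all accept a second biopsy and treatment does nothing:

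| Kappa | Conversion rate | Expected conversions | Chance of 6 or more |
|---|---|---|---|
| 0.6 | 0.70 × 0.40 = 0.28 | 16.8 | over 99% |
| 0.8 | 0.70 × 0.20 = 0.14 | 8.4 | 86% |
| 0.95 | 0.70 × 0.05 = 0.035 | 2.1 | 2% |

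Six is a useful marker. With no change possible in the other direction, an exact two-sided McNemar test gives p = 2 × 0.5^6 = 0.031. The protocol does not name this test; it is used here only to show how a paired test would behave. At kappa 0.8, the chance of six or more is 64% if p = 0.20 (40 women) and 94% if p = 0.50 (100 women). The problem is thus serious at moderate agreement and small at near-perfect agreement.

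**Endometritis.** A woman with endometritis and an abnormal ERA receives antibiotics and progesterone before the same re-biopsy. For her ERA result these two cannot be separated from each other either.

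**The case against.** The strongest reply concerns ERA. If section 9 is right that ERA is consistent across cycles, spontaneous conversion is rare and a before-after change is more informative; the kappa 0.95 row shows this. That stands in part and is why the point is weaker for ERA. But section 9 gives no figure, and it does not address women selected for a non-receptive result.

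The wording is also partly tentative: section 1.b speaks of hope, and 1.a of assessing. That stands too, and it is why a change of wording is enough. Section 8.a, however, says the repeat ERA is to determine an effect.

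A reader might infer several stronger things that the documents do not support:

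- *That the repeat microbiome is the only planned measure of whether the regimen works.* Pregnancy outcomes are followed for up to 5 years (section 2.a), and section 7.a adds an untreated group for them. The repeat test is the only planned measure of microbiome change.
- *That re-biopsy without treatment is ruled out.* Section 2.g and the physical well-being item of 8.a mention the repeat biopsy without naming treatment. Sections 2.a and the drug item of 8.a do tie it to treatment, and nowhere is an untreated comparison set up.
- *That the gap of some weeks between biopsies shows natural change.* Elapsed time shows only that change is possible.
- *That treatments are mixed in all women with endometritis.* Where only the microbiome is abnormal, the additions are probiotics after antibiotics, the same kind of combination as in the aim.
- *That the protocol classes an untreated re-biopsy as research.* The sentence "doing a repeat biopsy in this setting would be considered research- not standard of care" concerns a repeat biopsy in the setting of empiric progesterone.

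**Conclusion.** The concern holds as a mismatch between the stated aims and the design. As planned, the repeat biopsies can describe how often an abnormal result is normal after treatment; they cannot show that treatment caused the change. No later analysis can repair this, because the untreated re-tests are not part of the plan.

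It applies most clearly to the microbiome, on whose stability the documents are silent in both directions. It applies to ERA with less force. The size of the bias is unknown: every conversion, prevalence and agreement figure above is an assumption, and the range runs from negligible to enough to account for the whole observed change. The structural conclusion depends on none of those figures. It rests on reading sections 2.a and 8.a as placing the re-test after treatment, and on the absence of any described untreated re-test. The change should be made, but it does not call the patient-versus-control comparison into question.

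**What to change.** In sections 1.a, 1.b, 3.a and 8.a, replace the treatment-effect wording of the repeat-biopsy aims, separately for ERA and microbiome where each occurs, with: *to describe the proportion of women with an abnormal first result whose repeat result is normal after treatment, with a 95% confidence interval, reported as an uncontrolled before-after result*. Report women with endometritis separately.

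In section 1.b, soften the sentence on evidence for progesterone to say that the result is preliminary and cannot by itself show a treatment effect.

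The cost is text edits in four sections and weaker stated conclusions; no procedure, visit or assay is added. Keeping the causal wording would instead require a concurrent untreated re-test of women with the same abnormal result. That is a much larger change, and it is not asked for here.

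### Women with endometritis on the study biopsy stay among the cases with no stated case status, so an excess of altered microbiome could be credited to a new uterine factor when it reflects a condition standard care already treats

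*Protocol*

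**What the plan says.** **Detection.** For new patients, Protocol section 2.a takes the endometritis reading from the same biopsy that supplies the ERA and microbiome sample: "This endometrial biopsy will be sent to pathology to rule out endometritis as per clinical standard of care". For return patients it says "These patients will undergo an endometrial biopsy as above".

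**Handling.** A woman with endometritis on the first biopsy is "treated based on standard of care practice with routine use of oral antibiotics" and then biopsied again. If other results are abnormal, study treatments join that course: "for an abnormal ERA- vaginal progesterone would be added prior to rebiopsy". An abnormal microbiome adds probiotics in the same way. The same sentence gives the expectation about her microbiome: "EXPECTED that the microbiome will be altered in all endometritis patients".

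**Case definition.** Section 7.h has "unexplained infertility defined as normal ovarian reserve testing, normal ovulatory function, normal semen analysis" plus at least one patent tube, with no infection criterion. Recurrent loss is defined there by two or more unexplained early losses. Endometritis is not an exclusion, although another result from the biopsy day, a non-ovulatory progesterone level, is. Section 3.a counts infectious conditions in the evaluation after which most recurrent loss remains unexplained, and section 1.c describes the biopsy as standard care for ruling out endometrial infection.

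**Controls.** For the first control source, section 2.a says: "Egg freezing patients will undergo routine clinical evaluation which includes uterine ultrasound evaluation and ovarian reserve testing". The second source has a slightly longer list, given as follows: "elective sex selection patients will undergo a routine evaluation which includes a uterine cavity evaluation, ovarian reserve testing and blood testing". No endometritis evaluation is listed for either source, and no work-up is described for women recruited by flier. Whether control tissue is read for endometritis is not stated.

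**Intended inference.** Section 1.b hopes to suggest a uterine mechanism for an altered microbiome; section 3.a hopes to find a uterine factor not known before in unexplained infertility.

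**The concern.** The Protocol identifies a subgroup with a recognised, treatable condition, predicts that every member will be positive on one of the two study measurements, and leaves that subgroup among the unexplained cases. If the condition is commoner in cases than in controls, it produces a microbiome difference by itself. That difference would be genuine, but it would not be evidence of something new in women whose condition is unexplained; it would be endometritis, which the clinic already looks for and treats.

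The before-after part has a related difficulty. In a woman with endometritis, a routine antibiotic (not named) and progesterone and/or probiotics may all precede one re-biopsy. A change in her ERA cannot then be tied to progesterone alone, nor a change in her microbiome to the doxycycline-then-probiotic sequence, and these are the two treatment questions in section 1.b.

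**Working it through.** **1. Do the sections fit together?**

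| Question | Section | Answer |
|---|---|---|
| Is infection ruled out before recurrent loss is called unexplained? | 1.c, 3.a | Yes, it is part of the work-up |
| When is it ruled out for a new patient? | 2.a | On the study biopsy, after enrolment |
| What happens if endometritis is found? | 2.a | Treated and re-biopsied within the study |
| Is she excluded or reclassified? | 7.h | No |
| Does she still meet the infertility definition? | 7.h | Yes; it has no infection criterion |

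For recurrent loss, sections 3.a and 2.a pull against each other. For infertility there is no contradiction: a woman with endometritis simply meets the definition.

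**2. Size, as an illustration.** The Protocol plans 100 women per population (7.a) but gives no alpha, power, effect size, altered rate or endometritis prevalence, so there is no figure of its own to reproduce. Assumed inputs:

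- e, c: endometritis prevalence in cases and in controls
- b: altered rate without endometritis, the same in cases and controls
- every woman with endometritis altered, as section 2.a expects
- pooled two-proportion z-test, two-sided 5%, exact binomial enumeration, 100 v 100

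Case rate = e + (1 − e)b. Control rate = c + (1 − c)b.

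With b = 20%, c = 0:

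- e = 10%: 0.10 + 0.90 × 0.20 = 28% v 20%, gap 8 points, significant with probability 0.262
- e = 20%: 0.20 + 0.80 × 0.20 = 36% v 20%, gap 16 points, probability 0.719

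Sensitivity to the assumptions:

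| b | e | c | Gap (points) | P(significant) |
|---|---|---|---|---|
| 10% | 10% | 0 | 9 | 0.446 |
| 10% | 20% | 0 | 18 | 0.917 |
| 40% | 10% | 0 | 6 | 0.144 |
| 40% | 20% | 0 | 12 | 0.416 |
| 20% | 20% | 5% | 12 | 0.462 |
| 20% | 20% | 10% | 8 | 0.230 |
| 20% | 20% | 20% | 0 | 0.050 |

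If only 80% of women with endometritis are altered (b = 20%, e = 20%, c = 0), the case rate is 0.20 × 0.80 + 0.80 × 0.20 = 32%, the gap is 12 points and the probability 0.490.

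**3. Cost of restricting to endometritis-negative cases.** Suppose 20 of 100 cases have endometritis and the true rates without it are 40% v 20%.

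- 100 v 100: power 0.880
- 80 v 100: power 0.839
- 80 v 100 with 5% unread endometritis in controls: control rate 0.05 + 0.95 × 0.20 = 24%, so the 20-point difference appears as 16 points and power is 0.640

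A restriction on the case side only therefore understates a true difference.

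**The case against.** **The affected comparison is not a stated aim.** Section 1.b names healthy controls for gene expression only, and the directional hypothesis in 2.a concerns a non-receptive endometrium. This stands in part. The microbiome comparison has to be inferred from section 1.a, which asks whether patients have an altered microbiome, and from the mechanism claim in 1.b. It lowers the weight of the point but does not remove it.

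**The SAP may deal with it.** Stratifying or reporting with and without a subgroup is ordinary SAP content, and the SAP is not at hand. That is fair for the reporting. Who counts as an unexplained case, and whether control tissue is read, belong to the Protocol.

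**The size rests on assumption.** It does. Depending on prevalence, the gap can be nil or large.

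**Mixed treatments are not peculiar to endometritis.** True: section 2.a does not separate the pathways for a woman with both an abnormal ERA and an altered microbiome. Endometritis adds a further antibiotic course to the same problem.

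A reader might also infer more than the text supports:

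- *That the ERA comparison is distorted too.* The Protocol states no expectation that endometritis alters the ERA.
- *That an excess would be a false positive.* It would be a real difference; the risk lies in its interpretation.
- *That return patients' biopsies are not read by pathology.* The back-reference follows directly on the biopsy that is sent to pathology, the endometritis pathway is not limited to new patients, and section 8.a sends only a portion of the specimen for ERA and microbiome testing. The more natural reading is that they are read.

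**Conclusion.** The concern holds for the microbiome comparison and for attribution in the before-after results of women with endometritis. As written, the Protocol could credit a known and treated condition as a new uterine factor. It does so only if endometritis is commoner in cases than in controls, which the document neither states nor rules out. Under the assumptions above, a gap of 8 to 16 points is possible at a 20% background, with about a 26% to 72% chance of significance; the gap vanishes at equal prevalence. These figures show what could happen and do not estimate what will. The point should be settled because setting these women apart is inexpensive and changes what may be concluded. Confidence is medium, since the comparison is implied and no rates are given.

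**What to change.** 1. Reconcile Protocol sections 2.a, 3.a and 7.h by stating whether a woman with endometritis on the study biopsy counts as an unexplained case.
2. Using the pathology already obtained, report the microbiome comparison for all cases and for endometritis-negative cases side by side, with estimates and confidence intervals. Base any statement about a new factor in unexplained patients on the endometritis-negative estimate and its interval, not on whether significance is lost when cases are removed.
3. State whether control tissue is read for endometritis. If it is not, say that the restricted comparison is one-sided and may understate a difference.
4. Show endometritis patients as their own stratum in the before-after ERA and microbiome results.

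**Cost.** Wording, plus a split on a result that clinical care already produces. The restricted comparison has fewer cases: in the illustration, power falls from about 88% to 84%, or to about 64% if 5% of controls have unread endometritis. Reading control tissue would make the comparison symmetric but adds up to 100 pathology reads, so it is a choice to declare rather than a requirement of this point.

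**Separate item.** Section 2.a gives 2 weeks of vaginal probiotics, while section 5.a lists 10 days for one product, 14 days for another and no duration for the third. These passages need reconciling; this review takes no view on which is right.
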